Appendix 2: Myo tremor measurement guide

## **RESTING STATE TREMOR DETECTION**

# **Procedures:**

1. Plug the USB cable into laptop.

2. Strap the device to your hand (tremor dominant), with device on top of hand and cable protruding from the front of the device.

3. When it is connected, click the Icon "tremor" to run the program.

5. Use the dropdown menus to specify the time of your last dose. Provide the hour, minute, and AM/PM. Then click "Okay" to accept this entry and move on to the main program.

6. Click start to begin collecting data.

7. You will be shown an example of the hand movement to mimic: 1) finger tapping, 2) supination/pronation, and 3) 'screwing in a lightbulb'. For each sequence you be told to 'START' and 'STOP'. When the last sequence has run the program will indicate 'COMPLETE'.

8. Close the program (click the X button on the upper right corner) to finish.

# 1 Introduction

This Integrator Guide is the main technical reference for the recipients of the TremorGUI MATLAB package. This guide will walk through the

Note: There is no option to cancel collection. If this is desired, then close the program and begin again.

4. Perform the distraction task as instructed.

Note: Upon completion of a trial, the program will automatically save the data in multiple CSV files within the \private\data directory.

5. Export data by clicking the Export button.

🚺 Tremor							
Welcome Anon-User	Countdown Timer						
Control	Distraction Task						
Start							
Export	Press the SPACE bar when the colors match						
Click 'Start' to begin a trial or 'Export' to export data.							

The following occurs:

- All individual CSV files from \private\data are added to a new ZIP archive stored at the same location.
- The ZIP archive is named with time/date stamp range indicated the earliest and latest data files it contains. The application name and user tag from one of the data files is prepended to the ZIP archive name.
- The ZIP archive is saved primarily in the \private\data directory

• The user is then prompted to select a location on the computer where a copy of the ZIP is also saved. The default location is the user's Desktop directory. This can be reconfigured using TremorOpts.txt

When prompted, select a location to save the exported data archive. The default location is the Desktop. Click Save to save the data.

A Save exported data		e e e e e e e e e e e e e e e e e e e	×
🖉 🗢 🔳 Deskt	op 🕨 👻 🛃	Search Desktop	٩
File name:	Tremor_Anon-User_20170827-231614303_20170827-	231614303	•
Save as type:	(*.zip)		-
Browse Folders		Save Cancel	

- 6. Close the program to finish.
- 5 Options File

[figure not shown]
Tremor test:

**Device:** recording device, USB charging cable, USB hard lock, a connector allows you to transfer information from the device to the computer.

Appendix 3: Dermatology Photography Protocol

- 1. Ensure the patient did not apply make-up prior to having their picture taken. If the patient is wearing make-up, please make a note of this and have the patient remove make-up from the nasolabial folds (eye make-up is ok).
- 2. Have patient remove any jewelry including necklace, scarves, glasses, hat.
- 3. If needed, place headband to pull hair away from forehead
- 4. Position patient away from a direct light source and standing against a wall of neutral color
- 5. Instruct patient to have a relaxed facial expression with closed eyes and neutral lips
- 6. Stand approximately 1.5m from the patient with the camera in portrait position
- 7. Confirm camera settings- flash on, portrait orientation, and position camera in the same plane as the participants face.
- 8. Give instructions like, "slowly move your chin down" or "slowly turn your nose to the left" to achieve the desired pose.
- 9. Take 3 photos. Photos of the left and right side of the patient's face should span from the ear to nose in horizontal plane, and from the forehead to chin in the vertical plane. From center, include both patient's ears, forehead and chin. (see figure below)
- 10. Take additional photos of the ears and if one or more is out of focus
- 11. Upload photos to drive

Figure:

(a) right side

(b) center

(c) left side- not shown

#### CERTIFICATE OF ANALYSIS

Product: CBD Cannabis Extract Product Code: 1102 Lot Number: 1102 – 1507 – 03

	SPECIFICATION	RESULT
Potency (by GC)		
Cannabidiol (CBD)	≥25% w/w	59.34 %
Other Cannabinoids (by GC)		
Tetrahydrocannabivarin (THCV)	≤0.3% w/w	< 0.01 %
∆9-tetrahydrocannabinol (THC)	≤5% w/w	1.96 %
Cannabichromene (CBC)	≤5% w/w	2.10 %
Cannabigerol (CBG)	≤5% w/w	1.10 %
Cannabinol (CBN)	≤5% w/w	< 0.01 %
CBD:THC ratio	≥ 15:1	30 : 1
Residual Solvent (by GC)		00.1
Hexane	≤1% w/w	< 0.5 %
Loss on Drying (by IR radiation)		
Total Moisture & Volatile Impurities	≤6% w/w	0.32 %
Heavy Metals (by ICP-MS)		
Lead (Pb)	≤ 0.5 ppm	ND
Mercury (Hg)	≤ 1.5 ppm	ND
Cadmium (Cd)	≤ 0.5 ppm	ND
Arsenic (As)	≤ 1.5 ppm	ND
Aflatoxins		
AFB1	≤ 5 ppb	< 5 ppb
AFB1, AFB2, AGF1, AFG2	≤ 20 ppb	N D
Store in freezer.		

# Appendix 5

If subject is on this & CBD (which is metabolized by this enzyme) is added, the CBD level may be reduced CYP 3a4 inducers	If subject is on this & CBD (which is metabloized by this enzyme) is added then the CBD level may be higher	is metabolized by this enzyme) is added, the CBD level may be reduced	(which is metabloized by this enzyme) is added then the CBD level may be higher	Add CBD (which inhibits this enzyme) and the drug level may be increased CYP 3a4 substrates	Add CBD (which inhibits this enzyme) and the drug level may be increased CYP 2c19 substrates	Add CBD (which inhibits this enzyme) and the drug level may be increased	and the drug level may be increased	CBD (which is glucurondated by this enzyme) is added ther the CBD level may be higher	CBD (which is glucurondated by this enzyme) is added then the CBD level may be higher	glucurondated by this enzyme) is added then the CBD level may be higher	and starts any of these medications, CBD levels may decrease (CBD is glucurondated by this enzyme)	and starts any of these medications, CBD levels may decrease	concentrations can
Carbamazepine	Amiodarone	Aminoglutethimide	Chloramphenicol	Alfentanil (Alfenta)	Aripiprazole (abilify)	Acetaminophen	Azidothymidine		Cyclosporin A	ketoconazole	-	Gancyclovir	Phenobarbital
armodafinil	alprazolam	Artemisinin	amitriptyline	Alfuzosin (Uroxatral)	Carisoprodol (Soma)	diclofenac	clofibrate		Milk Thistle (Silymarin)	valproic acid		Phenobarbital	Phenytoin
bosentan	amlodipine	phenobarbital	armodafinil	Almotriptan (Axert)	Citalopram (Celexa)	ethinyl estidol	clorampehnicol		Niflumic acid	spironaldactone		Rifampin	Rasagiline
cisplatin	amprenavir	Carbamazepine (eg. Tegretol)	carbamazine	Alprazolam (Xanax)	Clobazam (Onfi)	flavipirido	Codeine		Tacromlimus (Prograf)			Tobacco Smoking	Rotigitine
cyclophosphamide	Anastrozole	Phenytoin (eg. Dilantin)	Cimetidine (Tagamet)	Amiodarone (Cordarone)	Clomipramine (Anafranil)	ibuprofen	Cyclosporin A			Amitryptline			Selegiline
Dexamethasone efavirenz	aprepitant atanazanavir	Primidone	Clopidogrel (Plavix) Delavirdine (Rescriptor)	Amlodipine (Norvasc) Aprepitant (Emend)	Clopidogrel (Plavix) Clozapine (Clozaril)	kampferol ketoprofen	Cyclosporin A diclofenac (Voltaren)			Ketoconazole			Valproic Acid
		Rifampin (eg. Rifadin)	Efavirenz (Sustiva)			ketoproten Isbotolol	Entacapone			clofibrate			
Ethosuximide etravirine	atorvastatin Azithromzcin	Rifapentine ST. John's wort	Esomeprazole (Nexium)	Atazanavir (Reyataz) Atorvastatin (Linitor)	Desipramine (Norpramin) Diazepam (Valium)	naproxen	Hydromorphone (Dilau	udid)		codeine			
felbamate	bicalutimde	prednisone	esomeprazole (Nexium)	Bepridil (Vascor)	Diphenhydramine (Benadryl)	Propranolol	ibuprofen			diazepam			
Glucocorticoids	boceprevir	ritonavir	etravirine	Bexarotene (Targretin)	Doxepin (Sinequan)	Propofol	ketoconazole?			dicofenac			
Griseofulvin	bromocriptine	valproic acid	Felbamate (Felbatol)	Bosentan (Tracleer)	Escitalopram (Lexapro)	phenylbutazone	ketoprofen			ibuprofen			
ifsofamide	Cannabinoids		Fluconazole (Diflucan)	Bromocriptine (Parlodel)	Fluoxetine (Prozac)	quercetin	Lorazepam (Ativan)			fluconazole			
lopinavir	chloroquine		Fluoxetime (Prozac)	Budesonide (Entocort)	Lansoprazole (Prevacid)	valproic acid	losartan			guanfacine			
methadone	cilostazol		Fluvoxamine	Buprenorphine (Subutex)	Lmipramine (Tofranil)		morphine			ketoprofen			
methlyprednisolone Modafinil	Cimetidine		imipramine indometharin	Bupropion (Zyban, Wellbutrin, V	Mephenytoin (Mesantoin) Methadone		morphine			methadone morphine			
Nafcillin	ciprofloxin		Indomethacin Isoniazid	Carbamazepine (eg, Tegretol) Cevimeline (Evoxac)	Methadone Moclobemide (Manerix)		nalaxone nalorphin			naproxen			
Nelfinavir	Clarithromycin		ketoconazole	Cilostazol (Pletal)	Nelfinavir (Viracept)		naltrexone			oxazepam			
Nevirapine	Clotrimazole		lansoprazole	Cisapride (Propulsid)	Olanzapine (Zyprexa)		naproxen			probenacid			
Oxcarbazepine	conavapin		Moclobemide (Manerix)	Clarithromycin (Biaxin)	Omeprazole (Prilosec)		Oxazepam			propofol			
Phenobarbital	conivaptan		Modafinil (Provigil)	Clonazepam (Klonopin)	Pantoprazxole(Protonix)		Oxycodone			ranitidine			
Phenylbutazone	crizotinib		norfluoxetine	Clopidogrel (Plavix)	Pentamidine		Tacrolimus (Prograf)			temazepam			
Phenytoin	crizotinib		Omeprazole (Prilosec)	Colchicine	Phenobarbital		temazepam			trimethoprim			
pioglitazone	Cyclosporine		oral contraceptives	Cyclophosphamide (Cytoxan)	Phenytoin (eg. Dilantin)		Tolcopone						
prednisone	Danazol		Oxcarbazepine (Trileptal)	Cyclosporine (Neoral) Dapsone (Avlosulfon)	Proguanil		zidovudine						
prednisone Primidone	darunavir Delavirdine		paroxetine ranitidine	Dapsone (Avlosulton) Darunavir (Prezista)	Propranolol (Inderal) R-warfarin (less active isomer)								
primidone	Dexamethasone		ritonavir	Dasatinib (Sprycel)	Rabeprazole (Aciphex)								
Progesterone	Diethyldithiocarbamate		Ticlopidine (Ticlid)	Delavirdine (Rescriptor)	Sertraline (Zoloft)			our PD natients are m	ore likely to be taking the	ise			
Rifabutin	Diltiazem		topiramate	Dexamethasone (Decadron)	Thalidomide								
Rifampin	Dirithyromycin		Voriconazole (Vfend)	Dihydroergotamine	Voriconazole (Vfend)			strong					
rifapentine	Disulfiram			Diltiazem (Cardizem)				moderate					
ritonavir	efavarinz			Disopyramide (Norpace)				weak					
ritonavir	Entacapone (high dose)			Docetaxel (Taxotere)									
Rofecoxib (mild)	Erythromycin			Donepezil (Aricept)									
Sulfadimidine	Ethinyl estradiol fasoamprinavir			Doxorubicin (Adriamycin) Droperidol									
	Fluconazole			Dutasteride (Avodart)		1							
Sulfinpyrazone Troglitazone	Fluoxetine			Ebastine (Kestine)		1							
	Fluvoaxamine			Efavirenz (Sustiva)									
	Gestodene			Eletriptan (Relpax)		ĺ							
	ginkgo			Eplerenone (Inspra)		]							
	goldenseal			Ergotamine (Ergomar)		]							
	Grapefruit juice			Erlotinib (Tarceva)									
	haloperidol			Erythromycin									
	imitinib			Estazolam (ProSom)									
	Indinavir Isoniazid			Eszopiclone (Lunesta) Ethinyl Estradiol		{							
	itraconazole			Ethosuximide (Zarontin)									
	itraconazole			Etoposide (Vepesid)									
	Ketoconazole			Exemestane (Aromasin)									
	lapatinib			Felodipine (Plendil)									
	lopinavir			Fentanyl (Sublimaze)									
	methadone			Finasteride (Proscar)									
	methlyprednisolone			Flurazepam (Dalmane)									
	Metronidazole Mibefradil			Fosamprenavir (Lexiva) Galantamine (Reminyl)									
	Mibetradil Miconazole	1		Galantamine (Reminyl) Gefitinib (Iressa)									
	most ***ivir meds			Granisetron (Kytril)									
	Nefazodone			Halofantrine (Halfan)									
	Nelfinavir			Ifosfamide (Ifex)									
	Nevirapine			Imatinib (Gleevec)									
	nifedipine			Indinavir (Crixivan)									
	nilobinib			Irinotecan (Camptosar)									
	Norfloxacin			Isradipine (DynaCirc)									
	Norfluoxetine Omeorazole			Itraconazole (Sporanox) Ixabepilone (Ixempra)									
	oral contraceptives			Ketoconazole (Nizoral)									
	Oxiconazole			Lapatinib (Tykerb)									
	Paroxetine (weak)			Levomethadyl (Orlaam)									
	pazopanib			Loperamide (Imodium)									
	phenobarbital			Lopinavir (Kaletra)									
	posaconazole			Loratadine (Claritin)									
	primaquine			Lovastatin (Mevacor)									
	Propoxyphene			Maraviroc (Selzentry)									
	prosaconazole			Mefloquine (Lariam)									
	Quinidine			Methylprednisolone Midazolam (Versed)									
	Quinine Quinupristine and dalfopristin			Midazolam (Versed) Mifepristone (Mifeprex)									
	Ranitidine			Modafinil (Provigil)									
	ranolazine			Nefazodone					1			1	
	riton			Nevirapine (Viramune)									
	Ritonavir			Nicardipine (Cardene)									
	ritonavir			Nifedipine (Adalat)									

Saquinavir	Nimodipine (Nimotop)	 	 	
saquinavir	Nisoldipine (Sular)	 	 	
Sertindole	Nitrendipine (Baypress)	 		
Sertraline	Oxybutynin (Ditropan)		 	
tacrolimus	Oxycodone (Percodan)			
tamoxifen	Paclitaxel (Taxol)			
telaprevir	Paricalcitol (Zemplar)			
telithromycin	Pimozide (Orap)			
ticagrelor	Pioglitazone			
tipranavir	Praziquantel (Biltricide)			
Troglitazone	Prednisolone			
Troleandomycin	Prednisone			
Valproic acid	Propoxyphene (Darvon)			
verapamil	Quazepam (Doral)			
voriconizole	Quetiapine (Seroquel)			
zafirlukast	Quinacrine			
zileuton	Quinidine			
	Quinine			
	Ranolazine (Ranexa)			
	Repaglinide (Prandin)			
	Rifabutin (Rimactane)			
	Ritonavir (Norvir)			
	Saquinavir (Invirase)			
	Sibutramine (Meridia)			
	Sildenafil (Viagra)			
	Simvastatin (Zocor)			
	Sirolimus (Rapamune)			
	Solifenacin (Vesicare)			
	Sufentanil (Sufenta)			
	Sunitinib (Sutent)			
	Tacrolimus (Prograf)			
	Tadalafil (Cialis)			
	Tamoxifen (Nolvadex)			
	Tamsulosin (Flomax)			
	Teniposide (Vumon)			
	Testosterone			
	Tiagabine (Gabitril)			
	Tinidazole (Tindamax)			
	Tipranavir (Aptivus)			
	Topiramate (Topamax)			
	Triazolam (Halcion)			
	Vardenafil (Levitra)			
	Verapamil (Calan)			
	Vinblastine (Velbane)			
	Vincristine (Oncovin)			
	Ziprasidone (Geodon)			
	Zolpidem (Ambien)			
	Zonisamide (Zonegran)			
	Zopiclone (Imovane)			
	Zopicione (intovane)			1

Appendix 6: Clinic visits procedures and duration During each clinic visit, participants will be given breaks every 1.5 hours and will be given lunch vouchers. 1. Screening visit

1. Screening visit	I	1
Screening visit	Time (min)	Note
Informed consent	45	PRA, PI
Eligibility Criteria	2	PRA, PI
Demographics	3	PRA
Medical History	10	PRA, PI
Family medical history	2	PRA
Concomitant Medications	10	PRA, PI
Assessment of past marijuana use	3	PRA
Drug, alcohol and tobacco abuse screening test	3	PRA
Drug Abuse-related AEs collection	2	PRA
MOCA	7	PRA
C-SSRS	2	PRA
Vital Signs , orthostatic BP, weight, height	10	PRA
Formal drug interaction assessment	3	PI
QUIP-RS	5	PI
Complete Physical Exam	10	PI
Neurological exam	10	PI
MDS-UPDRS part III, H&Y staging, Schwab & England Activities of Daily Living Scale	10	PI
Urinalysis	5	PRA
Blood draw for Hematology, hemoglobin A1C, CMP, cannabis test, serum pregnancy test if applicable	10	CTRC
ECG (12-LEAD)	10	CTRC
NPI	5	
Emotional and behavioral dyscontrol short form	2	Study subject
Tremor constancy and amplitude measure	5	PRA
Tremor measure device dispatched and instruction	10	PRA
Total visiting	184	Estimated visiting time-3 hours

# 2. Baseline visit

Baseline visit	Time	Note
Eligibility Criteria	1	PRA, PI
Medical History	2	PRA, PI
Concomitant Medications	2	PRA, PI
Randomization	1	PRA, PI
Alertness test	3	Study subject, before taking study drug
Vital Signs, orthostatic BP, height, weight	10	PRA, before taking study drug
Taking study drug	2	Study subject
Dispense study drug and instruction	10	PI
Adverse Events (b)	2	PRA, PI
Brief physcial exam (heart and lung ausculation)	5	PI
CGI	1	PI
MDS-UPDRS (all 4 parts), H&Y, Schwab & England Activities of Daily Living Scale	30	PI, Study subject
Unified Dyskinesia Rating Scale (UDysRS)	5	PI, Study subject
Vital Signs, orthostatic BP	10	PRA, one hour after taking study drug
Cognitive assessment battery	60	PRA
C-SSRS	2	PRA
NMSS	10	PRA
Home diary dispense and instruction	3	PRA
Tremor measure device dispatched and instruction	5	PRA
RBDSQ	2	Study subject
Anxiety short form	2	Study subject
Depression short form	2	Study subject
SCOPA-sleep	5	Study subject
Insomnia Severity Index (ISI)	2	Study subject
Modified Dysfunctional Beliefs and Attitudes about Sleep Questionnaire (DBAS-16)	3	Study subject
Pittsburgh Sleep Quality Index	3	Study subject
IRLS	2	Study subject
Fatigue severity scale	3	Study subject
Pain intensity and interference short form	2	Study subject
Bladder function-OABSS	3	Study subject
PDQ-39	7	Study subject
EQ-5D	2	Study subject

PGI-I	1	Study subject
Take picture of central face	5	PRA, Study subject
TUG	5	PRA, Study subject
Urine drug (THC) test, urine pregnancy test if applicable	5	PRA
Urine cups dispense and urine collection instruction	2	PRA
Tremor constancy and amplitude measure	5	PRA, 2 hours after taking study drug
Alertness test	3	Study subject, 3 hours after taking study drug
PSG equipment and data collected	2	PRA
Total time	230	estimated visiting time-3.5 hours

3. 1.25 mg/kg/day dose assessment visit

1.25 mg/kg/day dose assessment visit	Time	Note
Vital Signs, orthostatic BP	10	PRA, Begore taking study drug
Taking study drug in clinic	2	Study subject
Vital Signs, orthostatic BP	10	PRA, one hours after taking study drug
Medical History	2	PI, PRA
Concomitant Medications	2	PI, PRA
Adverse Events and drug abuse related AEs	2	
Withdrawal AEs, Liver function related AEs	3	PI, PRA
Complete Physical Exam	10	PI
Neurological exam	10	PI
QUIP-RS	5	PI
CGI	1	PI
MDS-UPDRS (all 4 parts), H&Y, Schwab &		
England Activities of Daily Living Scale	30	PI, Study subject
Unified Dyskinesia Rating Scale (UDysRS)	5	PI, Study subject
MOCA	10	PRA
TUG	5	PRA
NMSS	10	PRA
Home diary collection and review	2	PRA
Tremor constancy and amplitude measure (k)	5	PRA, 2 hours after taking study drug
Blinding assessment	1	PRA
Study drug compliance check	2	PRA
C-SSRS	2	PRA
RBDSQ	2	PRA
NPI	5	Signifant others
Anxiety short form	2	Study subject
Depression short form	2	Study subject
Emotional and behavioral dyscontrol short form	2	Study subject
SCOPA-sleep	5	Study subject
Insomnia Severity Index (ISI)	2	Study subject
Modified Dysfunctional Beliefs and Attitudes		
about Sleep Questionnaire (DBAS-16)	3	Study subject
Pittsburgh Sleep Quality Index	3	Study subject
IRLS	2	Study subject
Fatigue severity scale	3	Study subject
Pain intensity and interference short form	2	Study subject
Bladder function-OABSS	3	Study subject
PDQ-39	5	Study subject
EQ-5D	2	Study subject
PGI-I	1	Study subject

PGI-C	1	Study subject
Urinalysis, pregnancy test if applicable	5	PRA
Urinary collected for CBD and metabolites levels test	2	PRA
ECG (12-LEAD)	10	CTRC
Blood draw for Hematology, CMP, cannabis test	10	CTRC, 3 hours after taking study drug
Total visiting time	200	3.5 hours

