## **IV. Research Methods**

#### A. Outcome Measure(s):

**Primary Specific Aim:** To evaluate the efficacy of CBD on motor symptoms in PD. **Primary Outcome Measures:** Change of MDS-UPDRS Part III (motor examination) from baseline to the end of 2.5 mg/kg/day of CBD. MDS-UPDRS Part III assesses the motor signs of PD. **Secondary Specific Aim:** To examine safety and tolerability of CBD and the effect of CBD on severity and duration of tremor, night-time sleep, rigidity, emotional dyscontrol, anxiety, and pain in PD.

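### The baseline-visit timetable lists the MDS-UPDRS after the first dose, and nothing in the plan requires the primary outcome's starting value to be measured before it

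*Combined protocol and SAP*

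**What the plan says.** Section IV.A defines the primary outcome as "Change of MDS-UPDRS Part III (motor examination) from baseline to the end of 2.5 mg/kg/day of CBD". Section IV.F compares the mean change between arms with a two-sample t-test and presents pre- and post-treatment values by arm. The first dose is taken in clinic on Day 1, at the baseline visit (Section IV.C.1, Visit 2; Appendix 1).

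Appendix 6, item 2, is the only place that lists the procedures of this visit in sequence around the dose. Only the first alertness test and the first vital signs carry a pre-dose note, for example "PRA, before taking study drug". The dose row follows. After it come dispensing, adverse events, brief examination, CGI, "MDS-UPDRS (all 4 parts), H&Y, Schwab & England Activities of Daily Living Scale" and UDysRS, and then vital signs marked "PRA, one hour after taking study drug".

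The Visit 2 text in Section IV.C.1 names the MDS-UPDRS without a time relative to the dose. It mentions the first dose later, without ordering the two, and does not include the MDS-UPDRS among the items that may be done remotely beforehand. Appendix 1 footnotes k, n and t time the device tremor measure, vital signs and alertness test against the dose, but not the MDS-UPDRS. Part III is also rated at screening, up to 28 days before Day 1, but that score is not named as the baseline.

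**The concern.** A change score is a clean randomised comparison only if its starting value is unaffected by treatment. A rating made after randomisation and after the first dose may already contain an acute drug effect, and only in the CBD arm. Randomisation does not balance that. An early benefit would lower the CBD starting score and shrink the estimated effect. Early sedation or slowing would raise it and make the later change look larger. The same score would also be a poor baseline covariate in the longitudinal models that Section IV.F allows. Total MDS-UPDRS, the tremor items and the motor sub-scores come from the same rating, and CGI and UDysRS sit in the same block of the timetable.

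**Working it through.** **1. Timing from the Appendix 6 baseline rows (minutes, in listed order).**

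- Before the dose: eligibility 1 + history 2 + medications 2 + randomisation 1 + alertness 3 + vital signs 10 = 19. The dose takes 2, so it ends at minute 21.
- From the end of the dose to the start of the MDS-UPDRS: dispensing 10 + adverse events 2 + examination 5 + CGI 1 = 18.
- The MDS-UPDRS row takes 30: 18 to 48 minutes post-dose.
- UDysRS takes 5 and ends 53 minutes post-dose. The next row is the one-hour vital signs.

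This block therefore fits a real sequence. Section III expects the peak blood level at three hours, well after this window.

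**2. Does row order hold throughout?** No. All rows sum to 230 minutes. "Urine drug (THC) test, urine pregnancy test if applicable" starts at minute 213, which is 213 − 21 = 192 minutes post-dose, although a positive urine cannabis result at baseline is an exclusion (Section IV.C.1). The two-hour tremor measure starts at minute 220, which is 199 minutes post-dose. In the 1.25 mg/kg/day visit table, the one-hour vital signs directly follow the dose row.

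**3. The planned sample size.** Section IV.F gives an effect of 5.75 points, SD 6.72 and alpha 0.05 (sidedness not stated; two-sided reproduces the figures). The standardised effect is 5.75 / 6.72 = 0.856. The noncentral t calculation gives a total of 46 for 80% power and 60 for 90% (power 0.903 at 30 per arm). With 20% dropout, 46 / 0.8 = 57.5, rounded up to 58, and 60 / 0.8 = 75. All the stated figures are reproduced.

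**4. What a post-dose starting value would do.** Let D be the true CBD-minus-placebo benefit at the end of treatment, and a the acute CBD-minus-placebo benefit already present at the baseline rating. The expected difference in change scores is D − a. The documents give no value for a. As an assumption, write a = f × 5.75:

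| f (assumed) | Expected difference, 5.75 × (1 − f) | Power at 30 per arm |
|---|---|---|
| 0 | 5.75 | 0.903 |
| 5% | 5.46 | 0.872 |
| 10% | 5.18 | 0.835 |
| 20% | 4.60 | 0.741 |
| 30% | 4.03 | 0.626 |

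An acute worsening reverses the sign. With f = −10%, the expected difference is 5.75 × 1.10 = 6.33. With no lasting effect (D = 0) and the same acute worsening, it is 0.58 points rather than 0.

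**The case against.** The strongest reply is that Appendix 6 lists procedures and durations and does not prescribe an order. Step 2 of the working shows that its later rows cannot be in time order. The pre-dose notes appear only on alertness and vital signs, which are measured both before and after the dose, so their absence from the MDS-UPDRS row proves little. If list order counted, the Visit 2 text names the MDS-UPDRS before randomisation and before the first dose. All of this stands against any claim about how visits were run. It does not supply a rule: that text is not chronological either, since it places a two-hour post-dose tremor measure in the middle of its list. If row order is not binding, the timing of the primary baseline rating is simply unspecified.

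A reader might try to prove the post-dose placement from visit length, using "Study subject, 3 hours after taking study drug" and "estimated visiting time-3.5 hours". The final alertness test ends 183 minutes post-dose, and the earlier rows plus the dose take 21. That leaves 210 − 183 − 21 = 6 free pre-dose minutes in 3.5 hours, or 230 − 183 − 21 = 26 in the summed time, both under 30. The argument fails. Eligibility, history and medications (5 minutes) may be done remotely, which cuts the pre-dose rows to 14 and leaves 230 − 183 − 2 − 14 = 31. Part III with H&Y and Schwab & England takes only 10 minutes at screening. That fits within 26, and also within 210 − 183 − 2 − 14 = 11. The visit length is an estimate, and the task sum does not include the scheduled breaks.

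It is also fair that an effect 18 to 48 minutes after a single first dose may be small.

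**Conclusion.** The point holds as a defect in the written plan. The only sequenced timetable places the primary baseline rating after the dose, and no other section corrects it. Followed as listed, the pre-treatment value of the primary change score would be post-randomisation and post-dose, with possible contamination in one arm only. The direction is open and the size unknown. The figures in step 4 of the working rest entirely on an assumed f.

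Three stronger readings are not supported:

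- A reader might infer that participants were in fact rated on drug. The documents cannot show this, because the list is not chronological throughout.
- A reader might infer that the trial is underpowered. The planned 60 completers and 75 recruits reproduce, and would be unchanged with a pre-dose baseline. No passage supports a particular f.
- A reader might count as bias the different position of the MDS-UPDRS at the 2.5 mg/kg/day visit, where it is listed about 103 minutes after the dose and after the cognitive battery. That ordering is common to both arms and does not by itself bias the comparison.

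**What to change.** In Appendix 6 and the Visit 2 text of Section IV.C.1, state that the MDS-UPDRS (at minimum Part III), H&Y, CGI and UDysRS are completed before the first dose. Move the dose row below them, and say whether the row order is the order of conduct. Reconcile the Visit 2 text, Appendix 1 (including footnote k, which times the baseline device tremor measure after the dose) and Appendix 6. For anyone already rated after dosing, record the rating and dose times, and run a sensitivity analysis with the screening Part III score as the pre-dose reference. That score can be up to 28 days old, and it covers Part III only.

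The change needs no new procedure, staff or sample size. The three-hour observation starts later, so the visit lengthens by about 10 minutes if only Part III is moved (the screening duration, which includes H&Y and Schwab & England), or by 1 + 30 + 5 = 36, roughly 40, if all these ratings are. Items that may be done remotely offset part of this. Moving the 60-minute cognitive battery before the dose follows the same logic but is optional, because it adds more visit burden.
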